4.3 Supportive Care Guidelines

Supportive therapy for neutropenia:

If grade 3 or 4 neutropenia develops (ANC<1000/uL), G-CSF (Neupogen) can be administered, at the discretion of the treating investigator, until resolution of neutropenia. Neulasta (PEG-filgrastim) 6mg SC for 1 dose is recommended. If Neulasta is given, chemotherapy cannot be administered within 14 days. Neupogen can also be given at the discretion of the treating investigator. NOTE: Neupogen can be given any time before or after chemo. HOWEVER, Neulasta cannot be given within 14 days of chemotherapy.

Supportive therapy for neuropathy

Gabapentin or similar medications can be given at the discretion of the treating physician per institutional practice.

Dose Delays & Dose Modifications

Toxicities will be graded using NCI CTCAE version 4.03 (see Appendices). Dose delays and modification of lenvatinib and Eribulin are summarized below (for post-DLT period in phase II patients only). Individual patient dose reductions are also provided in separate tables.

Dose Delay & Modification for Eribulin and Lenvatinib

Toxicity	Adverse event	Dose Reduction/Delay	
		Eribulin	Lenvatinib
Hematologic toxicity attributed to any or all treatment	Platelets 75000-99999/mm ³ within 24 hrs prior to scheduled therapy	If Day 1: Hold until recovery of platelets >100,000/mm ³ . Resume at the same level after recovery If Day 8: No intervention	No dose modification necessary
	ANC <1000/mm ³ or Platelets 25000-74999/mm ³ within 24 hrs prior to scheduled therapy	If Day 1: Hold until recovery to ANC >1000/mm ³ and Platelets 100000/mm ³ . Resume at same level after recovery If Day 8: Hold until recovery to ANC >1000/mm ³ and Platelets 75000/mm ³ . Resume at same level after recovery	Hold until recovery to ANC >500/mm ³ and platelets more than 25000, Resume at same level after recovery.
	Platelets <25000/mm ³ or Platelets 25000-50000/mm ³ complicated by bleeding, easy bruising, petechiae, or requiring platelet transfusion	If Day 1: Hold until recovery to Platelets 100000/mm ³ . Resume at same level after recovery If Day 8: Hold until recovery to Platelets 75000/mm ³ . Resume at same level after recovery	Hold until recovery of Platelets 25000/mm ³ . Resume at current dose level.

	Prolonged neutropenia (ANC<500/mm ³ for >7 days)	Hold until recovery to ANC>1000/mm ³ . Resume at one dose level below current dose level	Hold until recovery to ANC>500/mm ³ . Resume at same level dose.

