	Febrile neutropenia (ANC <1000/mm ³ with temperature of >38.5°C)	Hold until recovery to ANC>1000/mm ³ . Resume at one dose level below current dose level	Hold until recovery to ANC>1000/mm ³ . Resume at same dose level
	Anemia	No reduction or delay	No reduction of delay
Hepatic toxicity	Grade 4 AST, ALT or Total Bilirubin Child Pugh Score	For patients with known liver dysfunction and Child Pugh score A, Eribulin should be started at a dose of 1.1mg/m ² . For patients with known liver dysfunction and Child Pugh score B, Eribulin should be started at a dose of 0.7mg/m ² . Eribulin should not be administered in patients with Child Pugh score C. If during treatment there is grade 3,4 liver toxicity then dose reduce by 1 dose level.	Hold until recovery to Grade 1 or baseline. Resume at reduced dose of 20 mg po daily if first occurrence, reduce to 14 mg po daily on second occurrence and 10 mg po daily on third occurrence.

Peripheral neuropathy	Grade 3 or 4	Hold until recover to \leq grade 2. Reduce dose by one dose level. If neuropathy fails to recover to grade 2 within 3 weeks, Eribulin should be discontinued.	No modifications necessary
Non-hematologic toxicity grade 3 or 4 attributed to any or all treatment (except for neuropathy)	Grade 3 or 4 nausea/vomiting despite optimal antiemetic treatment	Hold until nausea/vomiting have resolved to \leq grade 1. Resume at same dose level	Hold until nausea/vomiting have resolved to \leq grade 1. Resume at same dose.
	>Grade 2 stomatitis	Hold until stomatitis has resolved to \leq grade 1. Resume at one dose level below current dose level	Hold until recovery to \leq grade 1. Resume at the same dose level
Hypertension	Grade 3 Hypertension Or life threatening Hypertension	No dose modification necessary.	Withhold lenvatinib for Grade 3 hypertension that persists despite optimal antihypertensive therapy; resume at one dose level below current dose level. Discontinue for life threatening hypertension.
Cardiac dysfunction or Hemorrhage.	Grade 3 or Grade 4 events	No dose modification necessary	Withhold lenvatinib for development of Grade 3 event until improved to Grade 0 or 1 or baseline. Either resume at a reduced dose or discontinue lenvatinib depending on the severity and persistence of the adverse event.

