Proteinuria	>2 gms or less than 2 gms	No dose modification necessary.	Withhold lenvatinib for \leq 2 grams of proteinuria/24 hours. Resume at next dose level below current dose level; 2) when proteinuria is >2 gm/24 hours. Discontinue lenvatinib for nephrotic syndrome.
QTc Prolongation	Grade 3 or greater	No dose modification necessary	Monitor and correct electrolyte abnormalities in all patients. Withhold lenvatinib for the development of Grade 3 or greater QT interval prolongation. Resume lenvatinib at a one dose level below previous dose level when QT prolongation resolves to Grade 0 or 1 or baseline.

Day 8 dose of Eribulin may be delayed for a maximum of 1 week. If toxicities do not improve enough after 1 week delay then omit day 8 dose of Eribulin. If day 8 of Eribulin is omitted two consecutive cycles Eribulin should be resumed at one dose below current dose level.

Eribulin Dose Modifications

Starting dose and dose modifications for unacceptable toxicity that is thought to be related to Eribulin are listed below. Dose adjustments are to be made according to the greatest degree of toxicity. The most common toxic effects of Eribulin are fatigue, neutropenia (including neutropenic fever), peripheral neuropathy, and alopecia.

Eribulin Dose Modifications, TABLE 1

0	1.4
-1	1.1
-2	0.7

NOTE: Patients requiring a third dose reduction should be taken off study unless in the opinion of the investigator and/or the DSMB there is reason to believe that the patient is still experiencing clinical benefit (in such cases the DSMB will issue written approval).

Lenvatinib Dose Modifications

Recommended Dose Modifications for Persistent and Intolerable Grade 2 or Grade 3 Adverse Reactions or Grade 4 Laboratory Abnormalities, TABLE 2

0	20
-1	14
Note: Based on toxicity data of 1st 10 patients in Phase 2, starting Lenvatinib dose was not increased to 24 mg daily	

Other Toxicities with Lenvatinib

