11.1.2 Registering a Patient for the Safety run in Portion of the Study

For potential patients for the phase I portion of this study, please email the UT Health San Antonio Nurse/Research Coordinator *prior to consenting a patient* to determine whether a slot is available on the current cohort. An email confirming the reservation and expiration date will be sent by the UT Health San Antonio Nurse/Research Coordinator. In order for registrations to be processed efficiently, study teams are asked to inform the UT Health San Antonio Nurse/Research Coordinator of the date and time that the patient will need to be registered. Detailed instructions and project coordinator contact information regarding registration procedures will be provided separately from this protocol.

To register a patient, please complete and submit the following items to confirm eligibility and receive a subject identification number:

- Eligibility checklist (signed and dated by the treating physician)
- Signed and dated informed consent document
- Pathology Report

Affiliates sites are required to de-identify, scan, and e-mail the following source documents in order to confirm eligibility prior to registration for phase I patients:

- Complete medical and surgical history, current medications, history of clinically significant infections, and physical exam [including weight, height, ECOG PS, vital signs (pulse, temperature, respiratory rate, blood pressure, oxygen saturation)]
- Lab results (baseline CBC w/diff, baseline CMP)
- Documentation that archival tissue is available or documentation that a biopsy will be done
- Negative serum pregnancy test (if applicable)
- Copy of baseline imaging report

UT Health San Antonio study teams are NOT required to submit a separate email for UT Health San Antonio participants, provided that the required documentation listed above is readily available in the patient's electronic medical record (EMR). However, any information that is not available in the EMR must be de-identified and retained in the subject's research record.

The Nurse/Research Coordinator will review all source documentation required to confirm eligibility with the PI. Once confirmed, the Nurse/Research Coordinator will register the patient, assign a subject identification number, provide a cohort assignment, and send a confirmation of registration to the study team. Registration will then be complete and the patient may begin study treatment.

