DLT evaluation will occur weekly for the first cycle (1 cycle = 21 days).

Any enrolled and treated patient should be evaluated for DLT purposes.

The DLT period as a whole will be the first cycle of treatment. (Adverse events, however, will continue to be collected for the duration of treatment).

In general, a non-hematologic DLT is defined as any Grade ≥ 3 toxicity, and a hematologic DLT is defined as any Grade ≥ 4 toxicity, both by CTCAE v4.03 criteria.

In addition, the following criteria and exceptions apply:

- ANC $< 500/\text{mm}^3$ for > 7 days despite GCSF support is a DLT.
- Platelet count $< 20,000/\text{mm}^3$ for more than 3 days that is considered drug-related is a DLT.
- For nausea, vomiting, or diarrhea, patients must have Grade 3 or 4 toxicity that persists at this level despite use of optimal symptomatic treatment (per local institutional guidelines), in order for these to be considered a DLT.
- Grade 3 thromboembolic events are not considered DLT.
- Any Grade 3 rash that resolves to Grade ≤ 2 within a 10 day period (including with symptomatic treatment) will not be considered a DLT.
- Cases involving hyperbilirubinemia that is primarily indirect, and considered not reflective of underlying liver disease (ie, resulting from transfusion of red blood cells), will not be considered a DLT.
- A DLT must be attributed to one of the two investigational drugs. A “drug-related toxicity” includes as events, any toxicity considered related, probably related, or possibly related to study drugs. Toxicities clearly not related to the drug, such as disease progression, environmental, unrelated trauma may not be considered “drug related toxicity”

- As per the Mays Cancer Center DSMP, any protocol modifications, problematic safety reports, unanticipated problems, and suspension or early termination of a trial must be reported to the DSMB #2 and all members of the research team at UT Health San Antonio and all affiliate sites. Furthermore, the PI of this study will promptly notify all study affiliates, the UT Health San Antonio IRB, the Mays Cancer Center DSMC, and the FDA via a FDA Form 3500Aa written IND safety report of any adverse events that are either serious and/or unexpected. Suspension and early termination of a trial must also be reported immediately to the Director of Quality Assurance who will promptly notify the sponsor and the UT Health San Antonio IRB.

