Case Report Forms to be submitted during the 21 day DLT Evaluation Period (THIS IS ONLY A REQUIREMENT FOR PHASE I PATIENTS)

- Lab Results *No more than 48 hours after the 21 day DLT period ends*
- Adverse Events Form: *No more than 48 hours after the 21 day DLT period ends*
- Patient Vitals Form: *Each exam conducted during the DLT period, no more than 48 hours after the 21 day DLT period ends*
- Concomitant Medications Form: *Updated as necessary*
- Treatment Cycle Summary Form: *No later than 48 hours after the end of 21 day DLT period*

Case Report Forms to be submitted at the end of each cycle:

- Labs Results Form
- Master Adverse Events Form
- Patient Vitals Form
- Concomitant Medications Form: *Updated as needed*
- Treatment Cycle Summary Form

Case Report Forms to be submitted after every 2 cycles, when disease is assessed

- RECIST Disease Measurements Form: *Complete measurements for each assessment.*

Case Report Forms to be submitted no later than 1 week after End of Treatment Visit:

- Off-treatment Form:
- Patient Vitals Form
- Lab Results Form
- Master Adverse Events Form: *All AEs should be finalized within 30 days of last dose*

Case Report Forms to be completed during follow-up:

- Survival Status Form: Survival status and date of disease progression (if/when applicable) should be completed every 6 months until death.

V. Appendix – Table of Assessments

V. APPENDIX - DATA SUBMISSION TABLE

	Prior to registration	Within 5 days of registration	DLT Period-Only for Phase I Patients	After Each Cycle	After Every 2 cycles	End of Treatment Visit	Follow-Up
Eligibility Form	X						
Informed Consent Form	X						
Pathology Report	X						
On-Study Form		X					
Concomitant Medications Form		X ²		X ⁴			
Patient Vitals Form			X ³	X		X ⁵	
Labs Results Form			X ³	X			
AE Form		X ¹	X ³	X		X ⁵	
Treatment form			X ³	X			
Disease Measurement Form		X		X	X		
Off-Treatment Form						X ⁵	X ⁶
Survival Status Form							X ⁶

1 Should reflect all AEs present at baseline

2 Should reflect medications taken at baseline

3 Should be entered no more than 48 hours after the end of 21 day DLT period

4 Update as required

5 To be entered within 1 week of the end of treatment visit

6 Survival status and date of disease progression will be entered q 6 months until death or until pt withdraw

VI. Appendix SAE Reporting Form

VI. APPENDIX – EISAI SAE REPORT FORM

EISAI CLINICAL STUDY REPORT FORM FOR SERIOUS ADVERSE EVENTS & EVENTS OF SPECIAL INTEREST

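### Section 4.3 limits its dose-delay table to phase II patients after the DLT period, which conflicts with the table's own starting doses and, on either reading, leaves some patients or cycles outside it

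*Combined protocol and SAP*

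**What the plan says.** The scope of the table depends on several places in the combined protocol and SAP.

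- Section 4.3, Dose Delays & Dose Modifications: "Dose delays and modification of lenvatinib and Eribulin are summarized below (for post-DLT period in phase II patients only".
- Appendix III, Dose-Limiting Toxicity and Maximum Tolerated Dose: "The DLT period as a whole will be the first cycle of treatment", and "Any enrolled and treated patient should be evaluated for DLT purposes".
- Section 4.3, hepatic row of the table, eribulin column: "For patients with known liver dysfunction and Child Pugh score A, Eribulin should be started at a dose of" 1.1 mg/m². The row goes on to 0.7 mg/m² for class B and no eribulin for class C.
- Appendix V, column heading: "DLT Period-Only for Phase I Patients". Appendix IV says of the DLT-period forms: "THIS IS ONLY A REQUIREMENT FOR PHASE I PATIENTS".
- Section 11.1.2, on registering run-in patients: "For potential patients for the phase I portion of this study".
- Section 4.3, note under Table 2, explaining why lenvatinib stayed at 20 mg: "Based on toxicity data of 1st 10 patients in Phase 2".
- Section 4.2 requires laboratory tests in the two days before days 1 and 8 of every cycle, to check that treatment can go ahead safely.

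**The concern.** The Section 4.3 table is the only place that gives numeric neutrophil and platelet thresholds for holding and resuming eribulin. It also carries the eribulin hold rules for neuropathy and stomatitis. If it does not apply in cycle 1, a site with day 8 results in hand must decide without those thresholds. Sites that read the scope differently could then treat the same result differently.

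Neutropenia is the expected toxicity. The background in Section 1.2 reports it at grade 3 in 45.2% of eribulin patients in the phase III breast cancer trial, and at grade 3 or 4 in 54% and 64% in two phase II studies. Those are single-agent figures from other settings, and the documents give no rate for cycle 1.

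What is at stake is safe and consistent dosing of the remaining patients. The run-in dose decision has already been taken, and the efficacy test does not use the table.

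**Working it through.** **Design figures.** The point contains no power or alpha figure. For completeness, the exact binomial rule in Section 8.1.2 (n = 30, reject at 10 or more responses, 0.20 against 0.40) reproduces: alpha 0.0611 and power 0.8237. Neither depends on the dose table.

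**Timing.** The DLT period is cycle 1, which is 21 days. Eribulin is given on days 1 and 8. If the table starts after the DLT period, it starts at cycle 2 day 1, after both cycle 1 eribulin doses.

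**Internal conflict.** A starting dose is given on cycle 1 day 1. A table that begins at cycle 2 cannot set one, so the scope sentence and the hepatic row cannot both be followed literally.

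**The two readings.** Reading 1 takes Section 4.3 with Appendix III, so that every treated patient has a DLT period. Reading 2 takes it with Appendix V and Section 11.1.2, so that only run-in (phase I) patients have one.

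| Does the table apply? | Phase II, cycle 1 | Phase II, cycle 2 on | Run-in, cycle 1 | Run-in, cycle 2 on |
|---|---|---|---|---|
| Reading 1 | No | Yes | No | Only if run-in patients count as phase II |
| Reading 2 | Yes | Yes | No | Only if run-in patients count as phase II |

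The last column is unsettled because Section 11.1.2 calls the run-in phase I while the note under Table 2 places the first ten patients in phase 2. Neither row reads Yes throughout.

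**Remaining patients whose cycle 1 is outside the table.** The Synopsis gives 10 run-in and 30 phase II patients.
- Reading 2: 0.
- Reading 1, run-in counted within the 30: 30 − 10 = 20.
- Reading 1, run-in additional: (10 + 30) − 10 = 30.

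The figures 20 and 30 assume that nobody has enrolled since the run-in, so they are ceilings. In addition, up to 10 run-in patients could be outside the table in later cycles; the number still on treatment is not given.

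**What still applies in cycle 1 on reading 1.**
- The text before Table 1 covers eribulin starting dose and adjustment by worst toxicity, with no scope limit and no numeric trigger.
- The title of Table 2 gives grade triggers for lenvatinib.
- Section 6.0, footnote 11, gives the proteinuria rule.
- The label in Appendix I gives lenvatinib hold and reduction rules.
- Section 4.7 lets the physician stop therapy for safety.
- G-CSF for neutrophils below 1000 is discretionary.
- The day 8 delay rule allows one week, then omission, but names no count or grade.

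Missing are numeric neutrophil and platelet thresholds for eribulin and the table's graded rules for neuropathy and stomatitis.

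**Two rows that are wrong whatever the scope.**
- *Hepatic, lenvatinib.* The first occurrence resumes at 20 mg. Table 2 makes 20 mg the starting level, so the reduction is (20 − 20)/20 = 0%. Going to level −1 would be (20 − 14)/20 = 30%. The row also has a 10 mg step that Table 2 lacks; the label has it.
- *Proteinuria.* The row withholds at 2 g/24 h or less and resumes above 2 g. Footnote 11 and the label do the opposite: withhold at 2 g or more and resume at a lower dose below 2 g.

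**The case against.** The strongest reply is that reading 2 is the better one. Appendix V ties the DLT period to phase I patients, Sections 11.1.2 and 12.0 separate phase I from phase II patients, and the Appendix III sentence about any treated patient follows text on cohorts and MTD, so it may be only a run-in evaluability rule. The Child Pugh starting doses themselves suggest that cycle 1 was meant to be covered. Much of this stands, and it is why the count may be 0. It does not settle the matter: Appendix IV restricts form submission and not the DLT period itself, and reading 2 still leaves run-in patients outside.

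Three stronger inferences are tempting and are not supported.
- *Cycle 1 has no safety rules.* It has the partial cover listed in the working.
- *Patients with hepatic dysfunction will be overdosed.* Starting at 1.4 instead of 1.1 mg/m² would be 27% more (1.4/1.1 = 1.27), and instead of 0.7 mg/m², 100% more (1.4/0.7 = 2.00). But a site would have to disregard an explicit starting dose because of an introductory parenthesis, and cirrhosis and active chronic hepatitis are excluded in Section 3.1.
- *Neulasta given around day 8 would force omission of that dose.* Section 4.3 also bars Neulasta within 14 days of chemotherapy. After eribulin on day 1, that plainly read rules it out until day 15 (1 + 14). The rule applies in every cycle and does not arise from the scope sentence.

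It can also be said that the two faulty rows are a separate matter. That is correct: they are reported because they misdirect dosing in any cycle, and not as evidence on scope. The proteinuria row looks garbled in the available text, so a conversion fault cannot be excluded; the sponsor should check its master copy.

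**Conclusion.** The scope sentence is wrong as written. It conflicts with the starting doses in its own table, and on neither reading does the table reach all patients in all cycles. The practical gap is narrow: mainly numeric eribulin hold thresholds at cycle 1 day 8. Remaining patients whose cycle 1 is affected number 0 on reading 2 and at most 20 to 30 on reading 1. The documents do not establish which reading sites use, how many patients have enrolled, or how many run-in patients are still on treatment.

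A reader might infer that 20 to 30 patients will be treated without hold rules. The documents do not support that, since reading 2 is open to every site and many investigators would probably apply the table anyway. The lenvatinib hepatic row is wrong under any reading; so is the proteinuria row, if the text is as the sponsor wrote it. The point merits correction at the next amendment and has no bearing on sample size, alpha or power.

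**What to change.** Replace the parenthesis in Section 4.3 with: *applies to all patients (run-in and phase II) in all cycles, including cycle 1; a cycle 1 event meeting the Appendix III criteria is still recorded as a DLT.*

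In the same amendment, correct two rows:
- Hepatic, lenvatinib: make the first reduction 20 mg to 14 mg. Then either add 10 mg to Table 2 as level −2 or stop at 14 mg.
- Proteinuria: withhold at 2 g/24 h or more and resume one level lower below 2 g, as in footnote 11 and the label.

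Optional tidying: align the 24-hour laboratory window in the haematologic rows with the two-day window in Section 4.2.

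The cost is one amendment with one sentence, two rows and one decision on the 10 mg step, with no extra patients or procedures. The downside is that cycle 1 holds slightly lower the delivered dose behind the DLT assessment, so report those holds alongside it.

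### The Section 4.3 lenvatinib row for cardiac dysfunction or hemorrhage lists grade 4 events but omits the appended label's mandatory stop at grade 4, and its overlap with the platelet row needs a precedence sentence

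*Combined protocol and SAP*

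**What the plan says.** The dose table in Section 4.3 has a lenvatinib column, and two of its rows matter here. By its introduction, the table applies to phase II patients after the DLT period; Appendix III sets that period as the first 21-day cycle.

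- **Cardiac dysfunction or hemorrhage row.** The entry condition is "Grade 3 or Grade 4 events". The lenvatinib action is "Withhold lenvatinib for development of Grade 3 event until improved to Grade 0 or 1 or baseline", followed by "Either resume at a reduced dose or discontinue lenvatinib depending on the severity and persistence of the adverse event".
- **Platelet row.** It is entered at platelets below 25000/mm³, or at 25000-50000/mm³ when "complicated by bleeding, easy bruising, petechiae, or requiring platelet transfusion". The lenvatinib action is "Hold until recovery of Platelets 25000/mm"³, then "Resume at current dose level".

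The lenvatinib label reproduced in Appendix I gives three instructions for cardiac dysfunction or hemorrhage (label section 2.2): stop at grade 4, hold at grade 3 until recovery, then reduce or stop. The grade 4 stop is repeated in label section 5.2 for cardiac dysfunction and in the hemorrhage warning text. Label section 2.2 adds that it has no advice on resuming after a grade 4 clinical reaction has resolved.

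Section 4.7 ends study therapy for grade 4 toxicity that occurs after two dose modifications. It also ends therapy when the treating physician judges it necessary, including for safety.

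**The concern.** The main issue is the grade 4 event. The row admits it, but no action in the row is specific to it. The hold sentence names grade 3 alone, and the closing sentence, which has no grade in it, can be read as covering everything the row admits. On that reading a site may restart lenvatinib at a lower dose after a grade 4 bleed or grade 4 cardiac dysfunction, which the label in the same document rules out.

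The lesser issue is a patient with a grade 3 bleed whose platelets are in either range of the platelet row. That patient meets two rows with different restart doses, and nothing says which row governs lenvatinib. At stake are patient safety and uniform dosing across the sites of a multi-center trial.

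**Working it through.** The plan gives no figure to reproduce on this point. The check is a comparison of texts, followed by a rough size.

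**Grade 4 events**

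1. Appendix I, label section 2.2, has three instructions for this entry. The Section 4.3 row carries over two of them (the grade 3 hold and the choice to reduce or stop) and leaves out the grade 4 stop.
2. Section 4.3 does restate other label stop rules. The hypertension row keeps "Discontinue for life threatening hypertension", the proteinuria row keeps the stop for nephrotic syndrome, and the text on other toxicities keeps the stop for life-threatening perforation or fistula. The gap therefore looks like an omission, not a policy of leaving stop rules to the label.
3. Section 4.7 does not restore a mandatory stop. Its grade 4 criterion needs two earlier dose modifications, so a first grade 4 bleed falls to physician judgment.
4. The dose text in Section 4.3 refers to the appendices for toxicity grading. It does not say that the label overrides the table.

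**Grade 3 bleed with low platelets**

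1. Entry: the platelet row puts no limit on the grade of bleeding, so a grade 3 bleed in either platelet range meets both rows.
2. Hold: the platelet row releases lenvatinib at 25000. For a patient who enters at 25000-50000, that threshold is met on entry. The hemorrhage row still holds until the bleed improves. Both holds can be respected by taking the longer.
3. Restart: for a patient on 20 mg, the platelet row gives 20 mg. The hemorrhage row gives a reduced dose (14 mg, the next level in Table 2) or none. The reduction is (20 − 14)/20 = 30%. Taken literally, these cannot both be followed.
4. Tie-break: the one sentence in Section 4.3 that lets the greatest toxicity decide stands under the eribulin heading. It follows directly on a sentence about "dose modifications for unacceptable toxicity that is thought to be related to Eribulin". The lenvatinib part has no equivalent.

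**Size**

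The documents give no bleeding rate for the combination, so the following is an assumption. The label reports grade 3 or greater hemorrhage in 2% of 1108 patients on single-agent lenvatinib, at doses of 0.2-32 mg.

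- Any grade 3 or greater bleed: 30 × 0.02 = 0.6 patients expected. This is a ceiling under the assumption, because it counts cycle 1, which the table does not cover, and because grade 4 bleeds and bleeds with low platelets are both subsets. If the combination doubled the rate to 4%, the ceiling would be 30 × 0.04 = 1.2.
- Platelet overlap: take the label's 2% rate of grade 3-4 platelet decrease as a stand-in for the platelet row. Independence then gives 30 × 0.02 × 0.02 = 0.012 patients. Full overlap gives 0.6. Low platelets and bleeding are unlikely to be independent, so the value lies somewhere between.
- The 0.6 covers bleeding only. For the cardiac half of the row, the label's thyroid cancer trial reports grade 3 or greater dysfunction in 2%, so the same arithmetic gives a separate ceiling of 0.6, with grade 4 again only a part of it.

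**The case against.** **On grade 4.** The closing sentence follows a hold for grade 3, so it may concern grade 3 only; the row is then silent on grade 4 and permits nothing. If the sentence does reach grade 4, its reference to severity already points toward stopping. Table 2 is titled for grade 2 or 3 reactions and grade 4 laboratory abnormalities, so a grade 4 clinical event falls outside it. Section 4.7 limits therapy to the time before unacceptable toxicity and lets the physician stop for safety. The label is part of the protocol and is explicit. A reader might infer that the protocol directs a restart after a grade 4 bleed; for these reasons the documents do not support that. What stands is narrower: none of these texts makes the stop mandatory in the row that sites will use, and one plausible reading of the row allows a restart.

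**On the two rows.** The platelet row manages the count and the hemorrhage row manages the bleed. A patient with both problems would ordinarily be treated under both, and the event-specific row would set the restart dose. A reader might infer that the rows are irreconcilable and that patients with a grade 3 bleed would go back to full dose. A site would have to disregard the row headed for hemorrhage to do that, so this reading is not supported. What stands is the literal conflict in restart doses and the lack of a sentence that settles it.

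**On consequence.** Bleeds that qualify as serious adverse events are reported within 24 hours and reviewed by the DSMB. That oversight is real, but it does not supply the missing instruction.

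**Conclusion.** The point holds as a minor safety and consistency gap. Mainly, the cardiac dysfunction or hemorrhage row admits grade 4 events without the mandatory stop that the protocol's own appendix contains, and Section 4.7 does not supply one for a first event. Secondarily, the platelet and hemorrhage rows literally disagree on the restart dose after a grade 3 bleed; the natural reading resolves this, but the text should say so.

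Fewer than one affected patient is expected on the bleeding side if the single-agent 2% rate carries over to the combination, and the platelet overlap is rarer still. The grade 4 reading rests on the wording of Section 4.3 taken without the label, and that is its limit. It would be wrong to infer any effect on the trial's results: no endpoint, sample size or analysis depends on these rows.

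**What to change.** Make two wording changes in Section 4.3:

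1. In the cardiac dysfunction or hemorrhage row, lenvatinib column, add: *If the event is grade 4, stop lenvatinib permanently.* This brings the row into line with Appendix I.
2. Add one precedence sentence: *For any bleed of grade 3 or higher, the hemorrhage row governs lenvatinib, whatever the platelet count.*

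Leave the other cytopenia rules and Table 2 as they are; the limit in the title of Table 2 is useful. The cost is a protocol amendment with IRB approval, and no extra patients, visits or analyses.
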